## 6. RECRUITMENT METHODS

- *Describe the source of potential subjects*
- *Describe the methods that will be used to identify potential subjects*
- *Describe any materials that will be used to recruit subjects. A copy of any advertisements (flyers, radio scripts, etc.) should be submitted along with the protocol.*
- *If monetary compensation is to be offered, this should be indicated in the protocol*

To limit selection bias, and ensure true random selection, our Biostatistics Unit will randomly (using a random number generator) sample 400 patients from the 4,092 total patients.

**Recruitment:** The bilingual study RN, Multisite Patient Engagement Specialist or study coordinator will be responsible for recruitment at the various study sites. Given COVID-19 pandemic we will also be calling be patient over the phone to recruitment.

**Recruitment for Data Collection:** Eligible patients will be approached and called for consent (consent form 1) to have longitudinal data collected, including surveys at specified time points over the 12 months of their participation. Patients who are called will be give verbal consent. Next, bilingual study RN, Multisite Patient Engagement Specialist or study coordinator will obtain the randomization number from the Biostatistics Unit for the patient to determine if they were allocated to the DTM arm or COM arm. If the patient is randomized into the DTM arm, the recruiter will approach to obtain a second consent (consent form 2) to receive DTM. Verbal consent will be given for patients who are called for recruitment.

Informed consent will include a detailed but simple description, in patient's preferred language, of study risks/benefits.

**Recruitment for DTM:** Eligible patients will be approached or called for consent (consent 1) to have longitudinal data collected, including surveys at specified time

points over the 12 months from signing consent, in order to determine health outcomes. Next, the research coordinator will obtain the randomization number for the patient to determine if they were allocated to the DTM arm or COM arm. If the patient is randomized into the DTM arm, the coordinator will approach to obtain a second consent (consent 2) to receive DTM.

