Informed consent for DTM will include a detailed description, in English and Spanish, of the risks and benefits of the study with user-friendly images of the equipment. If the patients decline to participate in DTM, they will continue to receive standard of care and still have surveys administered and data collected over time (as agreed to in consent 1). Based on intention to treat (ITT), they nevertheless will be analyzed as part of the DTM group.

For those patients randomized to DTM, the RN will explain to the patients that if they agree to participate, they will be asked to measure vital signs daily, receive weekly telehealth “visits” with the telehealth RN (with appropriate assurances regarding confidentiality), and receive reminders of their weekly visits. The experienced bilingual RN will be trained in the proper recruitment of patients to eliminate selection bias based on a standardized protocol. The research RN will also explain to the DTM patient that s/he will have a bilingual trainer meet them at their home and that they will receive training on how to properly use the equipment.

For those patients randomized to COM, the research RN will have monthly phone contacts to determine how the patient is doing, how many days during the week they have been sick, and whether they have been to an unscheduled doctors visit, the ED or hospital during the last month and how many days they have been sick. Lastly, in both groups, the enroller will let patients know that they will be asked to complete pre and post surveys. The enroller will be trained on the proposed enrollment practices to ensure objective, unbiased and systematic selection and recruitment of participants.

DTM patients will be asked if they prefer to involve their caregiver; if patients agree, caregivers will be provided with the caregiver app (Figure 3). The bilingual enroller will explain to DTM patients that they will provide DTM training at their home.

We propose to study H/L patients with T2D, recruited from the Ambulatory Care Unit at LIJMC and the Division of General Internal Medicine Practice located in Queens NY, one of the most diverse populations in the world. We also propose to recruit at Southside Hospital. NUMC and Glen Cove Hospital as well as the Dolan Family Health Center. We selected these sites because 1) clinic patient statistics meet our enrollment criteria, with 4,092 adults H/L patients with T2D (well over the

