### INCLUSION AND EXCLUSION CRITERIA

**Inclusion criteria:** 1) H/L patients with a diagnosis of T2D alone or in combination with other chronic conditions (e.g., heart disease); 2) age > 18 speak English or Spanish.

Caregivers age >18 taking care of a patient with T2D alone or in combination with other chronic conditions.

Providers who treat patients with T2D alone or in a combination with other chronic conditions

**Exclusion criteria:** 1) patient is not a H/L with a diagnosis of T2D; 2) age <18.  
Identification of study participants: There are 4,092 H/L patients with T2D fitting our inclusion criteria.  
Caregivers age <18 who do not take care of a patient with T2D or in combination with other chronic conditions  
Providers who do not treat patients with T2D alone or in a combination with other chronic conditions.

Our goal is to enroll 224 (240, assuming a 10% attrition rate) patients/20-months. With a 50% acceptance rate (estimated on our previous enrollment experience), we will need to approach 400 total patients (or 20/month) to enroll 12 patients per month, easily reaching our goal of 224 participants over the 20-month accrual period.

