**1b. Quantitative approach.** This adaptation phase involves an ongoing formative process evaluation of usability using quantitative methods so that adjustments can be made as DTM is implemented. Below is how we will operationalize usability measures. **The first two usability variables will be collected upon subject enrollment in the RCT:**

**1bi. Rate of acceptability.** To simulate the rate of DTM acceptability in the real outpatient environment, we propose to determine, among those who DO NOT consent to be part of the study, the proportion who state that their reason is related to the technology (as opposed to those who simply do not want to be part of a study). This will allow us to compute the “acceptability rate” (as opposed to “acceptance rate” below). Data from other studies most similar to the intervention proposed herein indicate that telehealth acceptability in a general population may be as high as 96%. As acceptability may be different for the H/L disparity population, it is important to measure. Assuming the probability of acceptability in disparity populations is significantly lower (50% rather than 96%) and a total of 200 (240, assuming a 10% attrition rate) patients will need to be randomized (100 per arm) then, approximately 400 patients will need to be approached to yield 200 who consent to enroll. The actual acceptability rate will be calculated as  $X/200$ . Assuming the rate=50% and  $n=200$ , acceptability rate can be estimated to within +/- 7.1% using (95% CI for proportions).

**1bii. Rate of equipment acceptance:** Of those randomized to DTM, the rate of “acceptance” will be the % of patients who accept the app and peripherals. We will randomize 200 patients (240, assuming a 10% attrition rate), to yield a maximum of 100 patients per arm/3 years, the maximum number that can be treated with DTM over 6 months. Assuming 90% of DTM patients will constitute the usability sample, DTM acceptance is estimated +/- 6% (95% CI for proportions). ITT analysis will include all patients randomized to DTM. **The following usability variables will be collected during and upon completion of RCT:**

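### The DTM acceptability rate in 1bi is taken from people who do not consent to the study, with X and the 200 in X/200 undefined, so it cannot be read as acceptability of telehealth

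*Combined protocol and SAP*

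**What the plan says.** Section 12, 1bi, sets out to simulate acceptability of DTM in the real outpatient setting. It uses, "among those who DO NOT consent to be part of the study, the proportion who state that their reason is related to the technology", and separates these people from refusers with no interest in joining a study. The planning value follows: "Assuming the probability of acceptability in disparity populations is significantly lower (50% rather than 96"%), from which "approximately 400 patients will need to be approached to yield 200 who consent to enroll". Then: "The actual acceptability rate will be calculated as" X/200, with a stated precision of +/- 7.1% at 50% and n=200.

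1bii is a separate measure. Among those randomised to DTM, acceptance "will be the % of patients who accept the app and peripherals".

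Section 6 describes the consent sequence. Consent 1 covers data collection and surveys, randomisation follows, and for the DTM arm "the recruiter will approach to obtain a second consent (consent form 2) to receive DTM". It adds: "Informed consent for DTM will include a detailed description, in English and Spanish". Patients who decline DTM keep standard care, are still surveyed, and are analysed in the DTM group. The primary analysis text in Section 12 calls the design a modified Zelen method.

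Section 7 gives the 50% a different meaning: "With a 50% acceptance rate (estimated on our previous enrollment experience").

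**The concern.** Acceptability of telehealth should come from people who know what is on offer. 1bi appears to take it from people who refuse before DTM has been offered, and it misses those who see the equipment and reject it. The formula cannot be applied without guessing what X counts. Acceptability in this population is part of Specific Aim 1, and 1bi says it may differ from the 96% cited for a general population. As written, the result could not be set against that 96%, and two analysts could report different rates from the same data.

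**Working it through.** **1. The plan's own figures.** Inputs from 1bi: p = 0.50, n = 200. Half-width = z × √(p(1−p)/n).
- z = 2: 2 × √(0.25/200) = 7.07 points, the printed 7.1.
- z = 1.96: 6.93 points.
- Exact interval for 100/200: 42.9% to 57.1%, also 7.1 points either side.
- Number approached: 200/0.50 = 400.

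The arithmetic is sound. The question is what the proportion measures.

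**2. Who enters 1bi.** 1bi names no consent stage. Section 6 places the DTM offer after Consent 1 and randomisation, and keeps DTM decliners in the study. A person who does not consent to the study is therefore, by inference, a Consent 1 refuser.

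**3. What a Consent 1 refuser has been told.**
- Section 6 puts the detailed DTM description at the DTM consent. Section 24 asks that Consent 1 omit the full purpose and the randomisation procedure, for fear that patients allocated to the non-telehealth arm would decline. Both suggest that telehealth is not described at Consent 1.
- Sections 20 and 23 do not separate the two consents. They describe informed consent with pictures of the equipment and an explanation of every aspect of participation. Both suggest that it may be described.

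A technology-related reason can be interpreted only if the second account applies.

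**4. What X/200 could mean.** Inputs from 1bi: 400 approached and 200 enrolled, so 400 − 200 = 200 refusers. Let t be the number of refusers citing technology. The documents give no value, so a range is shown. The last column assumes that no consenter objects to the technology.

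| t (assumed) | X = technology refusals: t/200 | X = other refusals: 1 − t/200 | Share of those approached: 1 − t/400 |
|---|---|---|---|
| 0 | 0% | 100% | 100% |
| 16 | 8% | 92% | 96% |
| 100 | 50% | 50% | 75% |
| 200 | 100% | 0% | 50% |

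On the first reading the rate rises as acceptability falls. On the second the direction is right, but the 200 consenters are left out.

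**5. The two uses of 50%.** The enrolment rate is 200/400 = 50%. To obtain 400 approached from a 50% acceptability, acceptability has to be the probability that an approached patient enrols. Then 1 − t/400 = 50%, so t = 200 and every refusal is due to technology. 1bi's own distinction between technology and unwillingness to join a study allows for other refusals, and Section 7 bases the 50% on past enrolment.

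**6. Precision of a rate measured at Consent 2.** Arm sizes in the documents: 100 (1bii), 112 (Sample Size Justification), and 240/2 = 120 (1bii and the Figure 4 title). Half-width = 1.96 × √(p(1−p)/n), in points:

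| p | n=100 | n=112 | n=120 |
|---|---|---|---|
| 50% | 9.8 | 9.3 | 8.9 |
| 90% | 5.9 | 5.6 | 5.4 |

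**The case against.** **Disclosure.** A reader might infer that Consent 1 refusers know nothing of telehealth, so that their reasons are worthless. The documents do not support that. Section 24 withholds the full purpose and the randomisation procedure but says that people are told what they will be involved in at that stage, and Sections 20 and 23 mention equipment images. What matters is whether people were told of the technology, not whether it was formally offered. This objection stands: the timing is an inference and disclosure is unsettled.

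**Direction.** A reader might also infer that X/200 is shown to run backwards. It does so only if X counts technology-related refusals. 1bi says that proportion will allow the rate to be computed, so it may be an input. If X counts the other refusals, the direction is right. This also stands. However, any count among the 200 refusers still omits the 200 consenters.

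**Benchmark.** The share of those approached is an illustration. It treats all consenters as content with the technology, although they too may not have been told of it. The contrast of 75% with 50% is not a measured error.

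**Estimand.** 1bi deliberately separates acceptability among outpatients approached from acceptance among those randomised. A Consent 2 rate moves into 1bii's population, so it can supplement 1bi's aim but not reproduce it.

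**Other sources of reasons.** Section 12 promises CONSORT attrition reasons, discontinuation reasons, and exit interviews with DTM completers and dropouts. None clearly covers a patient who declines DTM and stays in follow-up.

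**Conclusion.** The point holds as a matter of definition and population, and it is minor. X/200 should not be reported as DTM acceptability: X and the 200 are undefined, the respondents are by inference Consent 1 refusers whose knowledge of telehealth is unclear, and patients who see DTM and decline it are excluded. The 50% cannot serve both as the acceptability behind the 400 approached and as the enrolment rate unless every refusal is technology-related.

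The size of any bias from disclosure cannot be computed from the documents. The only numerical indication is the illustration of 50% against 75% at an assumed 100 technology refusals. The printed 7.1% is not an arithmetic error; it simply does not carry over to a rate measured at Consent 2. A reader might infer that the trial's main comparison is weakened. It is not: 1bi is one descriptive Aim 1 usability measure, and neither 1bii as a count of uptake nor the HbA1c analysis depends on it.

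**What to change.** 1. Do not report X/200 as acceptability. Tabulate Consent 1 refusal reasons with the numbers approached and refusing, and label the 50% as the assumed enrolment rate.
2. Add a reason-for-declining field at Consent 2. Beside 1bii, report 1 − (technology-related declines / all DTM-randomised patients offered Consent 2). State the 95% half-width as about 8.9 to 9.8 points at 50%, or 5.4 to 5.9 points at 90%, for 120 down to 100 per arm, once the arm size is reconciled.
3. State what Consent 1 discloses about telehealth, and reconcile Sections 20 and 23 with Sections 6 and 24.
4. State that the new measure covers only people who already agreed to follow-up, so it supplements 1bi's aim of simulating the outpatient setting.

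The cost is wording and one data field. At 50% the half-width widens from 6.9 points (n=200, z=1.96) to 8.9 to 9.8, and the new rate shares its population with 1bii, differing from it only by the reason for declining.

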## 8. NUMBER OF SUBJECTS

- *Indicate the total number of subjects to be accrued locally. If applicable, distinguish between the number of subjects who are expected to be pre-screened, enrolled (consent obtained), randomized and complete the research procedures.*
- *If your study includes different cohorts, include the total number of subjects in each cohort.*
- *If this is multisite study, include total number of subjects across all sites.*

For the pilot test in Aim 1, we will have 12 subjects. For the RCT in Aim 2, we will randomize 224 patients. We plan to consent 224 patients assuming there will be a 10% attrition rate.

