**SECTION FIVE: SAMPLE SIZE JUSTIFICATION**

Our estimated sample size is 224 patients (240, assuming a 10% attrition rate): 112/group, yielding 80% power to detect a 0.5% difference in the pre-post change in HbA1c (two-tailed t-test with  $\alpha = .05$ ) over 6 months. Our power calculation is based on Polisena et al.'s meta-analysis. We computed a sample size-weighted median of the 12 standard deviations (SD) for HbA1c, yielding a value of 1.2%. If the SD of the pre-post 6-month change in HbA1c is 1.2% in each group, a 0.45% difference in this 6-month change yields a 0.42 effect size (ES). This ES is realistic, falling between 2 sets of reductions in the literature: the Diabetes Control and Complications Trial (1% decline in HbA1c reduced microvascular complications by 30%) and RCTs/meta-analyses citing reductions of 0.3% as "clinically significant". Our reduction of 0.45% falls between those limits, is clinically significant/meaningful, as patients can see improvements in their scores. In a systematic review of 13 RCTs (n=4,207) telehealth was associated with a clinically significant mean HbA1c decline of -0.44% compared to COM. In medically underserved patients, telehealth led to a net improvement in HbA1c, cholesterol, and BP. Although our main power calculation refers to our primary outcome (HbA1c), power is still acceptably high for secondary variables (SE, distress or QoL) such that 112 patients/group will yield 80% power to detect an effect size of 0.4 SDs, using a simple t-test to sample size and power.

Figure 4. Study Plan: Following 240 Patients for 12 Months Randomized to Either DTM (n=100) or COM (n=100) with 6 Month Intervention, Assuming 10% Attrition, Resulting in a Final Sample Size of 200

Year	2019												2020												2021												2022																																																	
Month	1	2	3	4	5	6	7	8	9	10	11	12	13	14	15	16	17	18	19	20	21	22	23	24	25	26	27	28	29	30	31	32	33	34	35	36	37	38	39	40	41	42																																												
Enrollment	CAB Focus Group: Confirm Outcomes, Preliminary Intervention Adaptions & Study Design												PAC Focus Group: Confirm Outcomes, Preliminary Intervention & Study Design Adaptions & Recommendations												Provider Focus Group: Pre-Pilot Adaptation Recommendations												CAB: PAC: Provider Focus Group Analysis												Pre-Pilot Adaptation Approval by the CAB																																					

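### The plan caps the arms at 100 patients, described as the most that can be treated with DTM, but randomises 112 or 120 per arm and attaches its 80% power to 112

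*Combined protocol and SAP*

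**What the plan says.** Section 12, item 1bii (rate of equipment acceptance), says "We will randomize 200 patients (240, assuming a 10% attrition rate"), and continues in the same sentence "to yield a maximum of 100 patients per arm/3 years, the maximum number that can be treated with DTM over 6 months". That item ends with the rule that "ITT analysis will include all patients randomized to DTM".

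Other places use different numbers:

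- Section 8: "For the RCT in Aim 2, we will randomize 224 patients", worded as if 10% attrition were already included.
- Section 7: 224, or 240 with 10% attrition.
- Section 12, Section Five: "Our estimated sample size is 224 patients (240, assuming a 10% attrition rate): 112/group, yielding 80% power to detect a 0.5% difference" in HbA1c change, by a "two-tailed t-test with" alpha 0.05. The same paragraph then works with a second difference: "If the SD of the pre-post 6-month change in HbA1c is 1.2% in each group, a 0.45% difference in this 6-month change".
- Section 12, tertiary analyses: 100 per group.
- Figure 4: 240 patients followed, arms of 100 and 100, and a final sample of 200 after 10% attrition.
- Section 5, item 1bi and the enrolment table after Figure 4: 200 (Section 5 and item 1bi add 240). Items 1biii, 1bv and 1bvii compute precision from 100 or 200.

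**The concern.** Most of the places that still say 100 or 200 give only a count. Item 1bii gives a reason: how many patients can be treated with DTM. Changing 100 to 112 there would leave open whether the programme can serve 112 or 120 people.

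Two things are at stake. If 100 limits the total number treated, some patients randomised to DTM may have no place. The intention-to-treat rule would keep them in the DTM arm and dilute the estimated effect. If 100 is the number left for analysis, the power quoted at 112 per group describes a larger sample than the one analysed. The plan says neither which applies nor what would happen to a DTM-arm patient after the hundredth.

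**Working it through.** **Inputs.** SD of the 6-month change 1.2%, two-sided alpha 0.05, differences 0.45% and 0.5%, and 112 per group, all from Section Five; the 100 from item 1bii; 10% attrition as stated. Equal allocation is taken from the per-group figures, so 240 means 120 per arm.

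**Reproducing 112.** Normal approximation: n per arm = 2 × (1.960 + 0.842)² × (SD/difference)².

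- 0.45%: 2 × 7.849 × (1.2/0.45)² = 111.6, so 112. This matches. The t-test gives 79.8% power at 112.
- 0.5%: 2 × 7.849 × (1.2/0.5)² = 90.4, so 91 (t-test 91.4, so 92). This does not match.

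So 112 comes from 0.45%, although the 80% claim is attached to 0.5%.

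**Gap to the stated maximum.** 112 − 100 = 12; 120 − 100 = 20.

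**Reading 1: 100 is the total who can be treated.** The upper bound assumes that every patient accepts DTM, that those without a place get no benefit, and that the SD stays at 1.2%. The effect is then multiplied by 100/112 or 100/120. Two-sample t-test power:

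| Randomised per arm | Treated with DTM | Power, 0.45% | Power, 0.5% |
|---|---|---|---|
| 112 | 112 | 79.8% | 87.4% |
| 112 | 100 | 70.4% | 79.2% |
| 120 | 100 | 67.4% | 76.4% |
| 100 | 100 | 75.1% | 83.4% |

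Item 1bii assumes that 90% of DTM patients form the usability sample. Taking that as uptake (an assumption), 0.9 × 112 = 100.8 and 0.9 × 120 = 108 would want DTM, so about 1 or 8 would lack a place. At 0.45% and 112 per arm, refusal alone (effect × 0.9) gives 71.05%, and adding the limit gives 70.36%, so the limit costs under one point. At 120 per arm the figures are 74.0% and 67.4%.

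**Reading 2: 100 is a limit at any one time.** With even accrual over the 20 months in Section 7 and 6 months of treatment, 112/20 × 6 = 33.6 and 120/20 × 6 = 36 patients are on DTM together. The limit does not bind.

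**Reading 3: 100 is what remains after attrition.** 100/0.9 = 111.1, so 112 per arm or 224 in total, which fits Section 8. 224 × 0.9 = 201.6, about 101 per arm. 240 × 0.9 = 216, or 108 per arm, which is not 100. Counting only patients with 6-month data, 101 per arm gives 75.6% power at 0.45% and 83.8% at 0.5%; 108 gives 78.3% and 86.2%. Keeping 112 evaluable would need 224/0.9 = 248.9, so 249 randomised, more than 240.

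**The case against.** The strongest reply is that nothing here is a supply limit. Item 1bii randomises 200 (240) in order to yield 100, which reads like a post-attrition count. Figure 4 likewise goes from 240 through 10% attrition to 200. The 100 is given per arm, so it covers COM as well, which uses no DTM place. The clause also mixes a 3-year span with a 6-month one. The likely cause is incomplete updating from 200 to 224. Much of this stands: the documents do not establish a shortage, and no section says that anyone would be refused DTM. It does not remove the conflict. The post-attrition reading fails for 240, and the clause still explains the number by treatment capacity. A patient who drops out after starting DTM has already used equipment and nurse time.

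The second reply is that 100 per arm still meets the power claim as stated, because at 0.5% it gives about 83%. That is right. The shortfall to about 75% applies to 0.45%, the difference from which 112 was derived. At 0.5%, power falls below 80% only if untreated patients are also counted in the DTM arm, and then to 79.2% or 76.4%.

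**Conclusion.** The per-arm numbers conflict and need correcting. A reader might go further and infer that 12 to 20 DTM patients will go untreated. The documents do not support that: those counts are upper bounds that need 100 to be a limit on the total and every patient to accept. They fall to about 1 or 8 at 90% uptake and to none under a limit at one time. A reader might also infer that the 80% claim requires 112 per arm. It does so only at 0.45%.

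Nor does a case follow for unequal allocation. Randomising 100 to DTM and 124 to COM gives 79.3% at 0.45% only with full uptake. At 90% uptake it gives 70.5%, against 70.4% for 112 per arm with 100 treated.

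What is established is that 100, 112 and 120 per arm cannot all be right, and that power with 100 per arm is about 75% at 0.45% or about 83% at 0.5%, given SD 1.2%, two-sided 0.05 and a t-test.

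**What to change.** 1. In item 1bii, say whether 100 is a limit on the total treated, a limit at one time, or the number expected to be evaluable, and confirm that DTM can be delivered to everyone randomised to it.
2. Use one randomised number and one evaluable number per arm in Sections 5, 7 and 8, and in Section 12 (the Aim 1 usability items, the tertiary analyses, Section Five, Figure 4 and the enrolment table), with attrition arithmetic that links the two.
3. If capacity is adequate, replace the 100 maximum with the number actually randomised to DTM.
4. If the arms are limited to 100, treated or evaluable, restate power for 100 per arm: about 75% at 0.45% or about 83% at 0.5%.
5. In either case, name the single difference on which the power claim rests.

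The cost is one factual answer about DTM capacity and a wording amendment. Nothing here by itself calls for more patients or a change to the randomisation list.
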